2	Average time between elranatamab or teclistamab claims	Sum of the days between claims for the index drug (continuous) divided by the total number of administrations -1	Index date to the end of follow-up Step-Up Dosing Period

	1	T	T
			Maintenance Periods
2	Frequency of elranatamab or	Total number of inpatient, non-IP, and pharmacy claims of the index drug during the	Index date to the end of follow-up
	teclistamab claims	time period based on vial size (continuous)	Step-Up Dosing Period
			Maintenance Periods
2	Relative Administration Intensity (RAI)	The ratio of the actual administrations received divided by the expected number of administrations according to the US label	Index date to the end of follow-up
		(continuous)	Step-Up Dosing Period
			Maintenance Periods
2	Time to Discontinuation (TTD)	Time in months from first administration until last administration prior to treatment discontinuation (continuous). Treatment discontinuation is defined as an 8-week gap in elranatamab or teclistamab therapy, next treatment after index treatment (CAR-T, BsABs, bendamustine or belantamab), or death.	Index date to the end of follow-up
2	Reason for Discontinuation	Reason for treatment discontinuation used to estimate time to discontinuation, either an 8-week gap in elranatamab or teclistamab therapy, next treatment after index treatment (CAR-T, BsABs, bendamustine or belantamab), or death.	Index date to the end of follow-up
Health care	resource utilization an	d costs	
3	All-cause IP visits	Medical claim for IP (non-emergency department [ED]) visit (dichotomous)	Start of data to 1 day before index date, index date until last recorded dose, and time from discontinuation through time of censoring
		Number of IP (non-ED) visits (continuous)	
3	All-cause OP visits	Medical claim for non-IP/non-ED visit (dichotomous)	Start of data to 1 day before index date, index date until last recorded dose, and time from
		Number of non-IP/non-ED visits (continuous)	discontinuation through time of censoring

3	All-cause ED visits	Medical claim for ED visit (dichotomous) Number of ED visits (continuous)	Start of data to 1 day before index date, index date until last recorded dose, and time from discontinuation through time of censoring
3	All-cause pharmacy claims	Pharmacy claim (dichotomous) Number of pharmacy claims (continuous)	Start of data to 1 day before index date, index date until last recorded dose, and time from discontinuation through time of censoring

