9.7. Data Analysis

This study will be largely descriptive in nature, and no formal statistical comparisons will be performed between groups. All characteristics and outcomes will be reported separately for each cohort. The number of patients who meet study eligibility criteria will be summarized in an attrition table. Inclusion and exclusion criteria will be listed hierarchically and the number of patients remaining at each step will be reported. Patient and treatment characteristics will be summarized using descriptive statistics. Categorical variables will be summarized by the number of available observations, frequency, percentage, and 95% confidence limits. Continuous variables will be summarized by the number of available observations, mean, standard deviation, 95% confidence limits, median, quartiles, minimum, and maximum, where appropriate. The prevalence and incidence, as well as the associated 95% confidence intervals (CI) for each adverse event, will be estimated. Kaplan-Meier methods will be used to estimate the median time to event, including 95% CIs for TTNT/D and OS. All-cause HCRU and MM-related HCRU will be measured as the mean, SD, median, IQR, minimum, and maximum of the total number of IP, OP, ED, and pharmacy claims. Given the variable follow-up time available for each patient, HCRU and costs will be reported, for instance, on a per-patient-per-month (PPPM) basis. Relative Administration Intensity (RAI) will be calculated as the ratio of the actual number of administrations during each time period divided by the expected number of administrations based on the label for the treatment.

Based on the study cohorts of interest, patients may be characterized by the following attributes of interest:

- Demographic characteristics such as age, sex, race/ethnicity, state, and region
- Reason for Medicare enrollment
- Social determinants of health such as household income, education level, marital status, and home ownership

PFIZER CONFIDENTIAL

- Clinical characteristics such as comorbidity and past treatment status
- Healthcare resource utilization such as hospitalization and place of service distribution

Subgroup analysis will identify samples of patients based on reason for Medicare entitlement: disabled beneficiaries, beneficiaries with end-stage renal disease (ESRD), and beneficiaries aged 65 to 115 years qualifying by age.

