9.7.1. Descriptive Analysis

Dichotomous and categorical variables will be summarized by the number and percentage of patients in each category. Continuous variables will be described using mean (SD), median (IQR), minimum, and maximum. If applicable, the frequency and percentage of patients with missing data for each variable will be described. Missing categorical data will be included as a separate "missing" category. Missing continuous data will not be included in the summaries and analyses (i.e., only non-missing data will be analyzed). No imputations will be performed.

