9.7.3. Healthcare Resource Utilization and Cost

All-cause HCRU and MM-related HCRU (i.e., HCRU with a diagnosis code or treatment for MM) will be measured as the total number of per-patient-per-month (PPPM) IP, OP, ED, and pharmacy claims that occurred over the follow-up period. Medical claims will only be counted once per day to estimate visits. Additionally, the total length of IP stays will be reported among patients with at least one IP visit. Given the recency of the study period, costs will not be adjusted for inflation.

HCRU and costs will be measured across three different time periods: from the start of data to a day before the index date, from the index date until last recorded dose, and the time from discontinuation through the time of censoring. Patients will be censored at the earliest of death, next treatment (CART, BsABs, bendamustine or belantamab), the end of part A or B continuous closed-claim coverage, or the end of data.

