9.7.5. Time to Discontinuation

Prior to the assessment of this outcome, the average follow-up time will be assessed; if the study team deems that the follow-up time is adequate, then TTD will be assessed. TTD is the total amount of time from the index date until the date of discontinuation; treatment discontinuation is defined as an 8-week gap in elranatamab or teclistamab, next treatment after index treatment (CAR-T, BsABs, bendamustine or belantamab), or death. TTD will be assessed as the time in months (1 month = 30.4375 days) using Kaplan-Meier methods. Median time-to-event will be reported along with the IQR. The 95% confidence intervals (CI) for the median time-to-event will be calculated using log-log transformation. Results will be depicted graphically by Kaplan-Meier curves. Patients who do not have a recorded discontinuation event or death will be censored on the earliest of the end of continuous closed-claim coverage or end of data. The percentage of patients who reached the outcome, as well as the percentage of censored patients, will be reported.

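### On-treatment HCRU and cost per patient-month end at the last recorded dose, so one-dose patients have a 0- or 1-day denominator and the planned mean, SD and maximum are unstable

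*Protocol*

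**What the plan says.** Section 9.7.3 splits HCRU and cost into three periods. After the pre-index period, the other two run "from the index date until last recorded dose, and the time from discontinuation through the time of censoring". Table 3 in section 9.3 repeats this for the HCRU and cost variables: "Start of data to 1 day before index date, index date until last recorded dose, and time from discontinuation through time of censoring".

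On the scale, section 9.7 says that "HCRU and costs will be reported, for instance, on a per-patient-per-month (PPPM) basis". On the statistics, it says that HCRU "will be measured as the mean, SD, median, IQR, minimum, and maximum of the total number of IP, OP, ED, and pharmacy claims". Section 9.7.1 applies the same kind of list to continuous variables in general, which covers cost: "Continuous variables will be described using mean (SD), median (IQR), minimum, and maximum". It also leaves missing continuous values out and imputes nothing.

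The opening paragraph of section 9.7.3 describes the period differently. There the per-month figures are for "claims that occurred over the follow-up period", not for three separate windows.

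Section 9.2.1 admits a patient with a single claim for the index drug. It also requires 30 days of enrolment after index, but that rule concerns coverage and does not lengthen the index-to-last-dose window.

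**The concern.** HCRU and cost are primary Objective 3. A rate per month divides by the length of the window, and here that length is set by how long the patient kept receiving the drug. For a patient whose only dose is the index dose, the window is 0 days if dates are subtracted and 1 day if they are counted inclusively. The protocol does not say which applies.

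Neither outcome is good. Under the first, the ratio is undefined, and the rule on missing continuous values could remove exactly the patients who stopped earliest. Under the second, one admission becomes about 30 per month and its whole cost is scaled up with it. Early use is also likely to cluster in these short windows: Table 2 expects inpatient administration to be possible at the index, second and third treatment dates. In a mean of patient-level rates, a 1-day window counts as much as a year-long one.

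**Working it through.** The protocol states no per-month figure, no single-dose share and no utilisation rate, so there is no published number to reproduce. What follows is direct arithmetic.

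**Inputs from the protocol.** Window: index to last recorded dose (9.7.3, Table 3). Minimum doses: one (9.2.1). Visit counting: "Medical claims will only be counted once per day to estimate visits". Month length: "1 month = 30.4375 days", which section 9.7.5 states for time to discontinuation and which is assumed here for the per-month scale. Cohort size for illustration: 133 (9.5). Dosing frequency: Table 4.

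**Assumptions.** k = 1, 3, 7 or 13 single-dose patients, each with a 1-day window and one index-day event. All others are on treatment for 6 months at a fixed rate r or, for dose-proportional items, receive 24 doses with the last on day 155 (the second step-up dose is taken to fall on day 4).

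**Formulas.**
- Patient rate = events ÷ (window days ÷ 30.4375).
- Mean of patient rates = [k × 30.4375 + (133 − k) × r] ÷ 133.
- Pooled rate = total events ÷ total patient-months.

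**Step 1, single patients.** One event in 1 day gives 30.44 per month. In doses per month, stopping after two doses (day 4) gives 2 ÷ 4 × 30.4375 = 15.2, and after three (day 8) 3 ÷ 8 × 30.4375 = 11.4. The patient with 24 doses has 24 ÷ 155 × 30.4375 = 4.71. The inflation fades with time on drug and is not confined to single-dose patients.

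**Step 2, effect on the mean.** Each index-day event in a single-dose patient adds 30.44 ÷ 133 = 0.23.

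**Step 3, infrequent event, r = 0.5 admissions per month.** For k = 3 the mean is (91.31 + 65) ÷ 133 = 1.18. The pooled rate is (3 + 390) ÷ (0.099 + 780) = 0.504.

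| Single-dose patients | Mean of patient rates | Pooled rate | Their share of the sum behind the mean |
|---|---|---|---|
| 1 (0.8%) | 0.73 | 0.501 | 32% |
| 3 (2.3%) | 1.18 | 0.504 | 58% |
| 7 (5.3%) | 2.08 | 0.509 | 77% |
| 13 (9.8%) | 3.43 | 0.518 | 87% |

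The share runs from 54% to 94% at r = 0.2, and from 19% to 77% at r = 1.0. Single-dose patients supply more than half of the sum from k = 1, 3 and 5 for r = 0.2, 0.5 and 1.0.

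**Step 4, dose-proportional item, others at 4.71 units per month.**

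| Single-dose patients | Mean of patient rates | Pooled rate | Their share of the sum behind the mean |
|---|---|---|---|
| 1 | 4.91 | 4.71 | 5% |
| 3 | 5.29 | 4.72 | 13% |
| 7 | 6.07 | 4.72 | 26% |
| 13 | 7.23 | 4.73 | 41% |

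The ratio of mean to pooled rate runs from 4.91 ÷ 4.71 = 1.04 to 7.23 ÷ 4.73 = 1.53. Half of the sum is passed only at 18 patients (13.5%).

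**Step 5, the median.** It stays at 0.5 in step 3 and at 4.71 in step 4 for every k.

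**The case against.** The strongest reply is that the protocol does not fix the estimator. In section 9.7 the list of statistics is attached to total numbers of claims. The per-month scale comes in a separate sentence and only as an example. A pooled rate would barely move, and the formula, the day count and the handling of a zero denominator could be left to the statistical analysis plan. This stands in part: a mean of patient rates is an inference, though a natural one, because a pooled rate has no between-patient SD, minimum or maximum. It does not dispose of the point. The protocol itself sets both the window and the patient-level statistics, and section 9.8 says that it will be strictly followed.

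Two further replies are sound. The median and IQR are already planned and hardly change, and the study is descriptive, so no test depends on the mean. Also, the mean of patient rates and the pooled rate answer different questions: the average patient against the average month of treatment.

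A reader might infer that single-dose patients will dominate every on-treatment mean, or that the inflation can be put at a definite multiple. The documents support neither. They give no single-dose share, no utilisation rate and no treatment duration. With a 0-day window such a patient drops out and cannot dominate. For frequent or dose-driven items the shift is modest.

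**Conclusion.** The point holds as one of instability. Followed as written, with per-month scaling, the plan gives single-dose patients an undefined or 1-day denominator in a primary-objective result and has no rule for it. The mean, SD and maximum are exposed. The exposure is strong for infrequent events such as inpatient visits, where three patients in 133 can more than double the mean (1.18 against 0.504). It is modest for dose-proportional items, at about 1.04- to 1.5-fold for 1 to 13 patients.

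These sizes rest on assumed shares and rates, equal 6-month or 24-dose treatment in everyone else, and the inclusive day count. They show how sensitive the mean is and do not forecast the result. Separately, section 9.7.3 contradicts itself on whether the denominator is the whole follow-up period or each of three windows.

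**What to change.** In section 9.7.3:

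- Report as the headline per-month figure, for each window, total visits (or total cost) divided by total patient-months over the cohort, with a 95% confidence interval from a bootstrap that resamples patients.
- Keep the per-patient distribution as median and IQR.
- State an inclusive day count for the on-treatment window (last dose minus index, plus 1), so that no patient is dropped for a zero denominator.
- Reconcile the sentence that counts claims over the follow-up period with the three windows that come after it.

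The cost is a few lines of text and a bootstrap; no new data are needed. The downside is small: the pooled rate gives more weight to patients treated for longer and has no simple between-patient SD. The change should be in place before the final analysis, which the milestones put at 27 February 2026.

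### The HCRU and cost windows are not contiguous: the on-treatment window ends at the last dose, the next starts at discontinuation, and the days between enter no listed window

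*Protocol*

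**What the plan says.** Section 9.7.3 of the protocol sets three periods for HCRU and cost. The first runs from the start of data to the day before index. The other two run "from the index date until last recorded dose, and the time from discontinuation through the time of censoring". The HCRU and cost rows of Table 3 (section 9.3) repeat this as "Start of data to 1 day before index date, index date until last recorded dose, and time from discontinuation through time of censoring". The rows for total HCRU and total MM-related cost use the same three periods, and no row lists a whole-follow-up period.

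Section 9.7.5 says that "treatment discontinuation is defined as an 8-week gap in elranatamab or teclistamab, next treatment after index treatment", or death. It adds that "TTD is the total amount of time from the index date until the date of discontinuation". The TTD row of Table 3 has a different endpoint: "Time in months from first administration until last administration prior to treatment" discontinuation.

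On censoring for HCRU, section 9.7.3 says: "Patients will be censored at the earliest of death, next treatment (CART, BsABs, bendamustine or belantamab"), with end of Part A or B coverage and end of data as the other two reasons. Its opening sentence describes the measure as per-patient-per-month "claims that occurred over the follow-up period".

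**The concern.** The second window closes at one anchor (last recorded dose) and the third opens at another (discontinuation). All three discontinuation events come after the last dose, so the interval between the anchors has no home. For death and next treatment the third window is also empty, because the event that opens it is the event that censors the patient.

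HCRU and cost are Primary Objective 3, and the omitted days are not a random sample: they are tied to stopping, switching and dying. Section 9.7.6 treats the same interval as relevant to safety, following adverse events to 14 or 90 days after the last administration. An infection admission 10 days after the last dose, in a patient who dies on day 20, would count as a safety event, yet its cost would enter no HCRU period.

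**Working it through.** The protocol states no figure to reproduce. The check is a day count on its own definitions.

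**Inputs from the protocol**
- Window 2: index to last recorded dose (9.7.3, Table 3).
- Window 3: discontinuation to censoring (9.7.3, Table 3).
- Discontinuation: 8-week gap (56 days), next treatment or death (9.7.5).
- HCRU censoring: death, next treatment, end of Part A or B coverage, end of data (9.7.3).
- One month = 30.4375 days (9.7.5).

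**Assumed for illustration:** last dose on day 168 after index, and the event days shown below.

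**Formula:** uncovered days = censoring day − length of window 2 − length of window 3.

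**Reading (a): discontinuation dated at the qualifying event, a gap being dated when it completes**

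| Patient | Window 2 | Window 3 | Uncovered |
|---|---|---|---|
| 8-week gap, followed to day 300 | 168 | 300 − (168 + 56) = 76 | 300 − 168 − 76 = 56 |
| Death 20 days after last dose (day 188) | 168 | 188 − 188 = 0 | 188 − 168 − 0 = 20 |
| Next treatment 35 days after last dose (day 203) | 168 | 203 − 203 = 0 | 203 − 168 − 0 = 35 |
| On treatment, end of data 7 days after last dose (day 175) | 168 | none | 175 − 168 = 7 |

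The maximum for a gap discontinuer is 56 / 30.4375 = 1.84 months. As a share of time from index to discontinuation it is 56 / (L + 56), where L is the day of the last dose: 67% for L = 28, 40% for L = 84, 25% for L = 168 and 14% for L = 336.

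**Reading (b): discontinuation back-dated to the last dose.** Window 3 becomes 300 − 168 = 132, 188 − 168 = 20 and 203 − 168 = 35 days in the first three cases, leaving 0 uncovered. The fourth patient has no discontinuation event and still has 7 uncovered days.

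**Effect on the estimates.** Let C and T be the claims (or cost) and person-time inside the windows, and c and t those on the dropped days. A total summed over the windows is C instead of C + c, so it can only be too low. The monthly rate is C / T instead of (C + c) / (T + t). It is too low if c / t exceeds C / T, and too high if c / t is smaller. The protocol gives none of these four quantities.

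**The case against.** Three arguments can be made for the plan.

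**Back-dating.** The TTD row of Table 3 measures to the last administration. If discontinuation is dated there, window 3 starts at the last dose and the gap closes for every patient with a discontinuation event. This stands as a possible reading, and it shows that the unsettled discontinuation date is part of the defect. It does not rescue the text. The row places the last administration before discontinuation and so treats them as two dates; 9.7.5 measures to the discontinuation date; and 9.7.3 does not mention back-dating. Patients censored on treatment have uncovered days under either reading.

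**Whole follow-up.** The opening sentence of 9.7.3 refers to the follow-up period, which section 9.2 runs from index to death, end of study period or end of enrolment. That could support an overall total containing these days. Table 3 lists no such period, even for totals, and section 9.8 commits the analysts to following the protocol strictly. The point is ambiguous, not resolved.

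**Direction of bias.** A reader might infer that cost is biased low, and most for the patients who do worst, because the dropped days can include terminal admissions. The documents do not support that for monthly rates. Person-time drops out with the claims, and window 2 carries the step-up and weekly study-drug administrations (Table 4), whereas the dropped days carry none. The net direction cannot be derived. This objection stands in full for per-patient-per-month values, but not for summed totals.

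**Conclusion.** The point holds on the plain wording of 9.7.3, Table 3 and 9.7.5. Under event dating, the uncovered time is up to 56 days (1.84 months) for a gap discontinuer. For a patient who dies or switches before the gap completes, it is every day from last dose to event. For a patient censored on treatment, it is the days since the last dose, whichever reading is used.

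Visits, inpatient days and costs summed over the windows are understated to the extent that anything was billed on those days. Per-patient-per-month values are distorted in a direction that depends on whether the dropped days are costlier than the retained ones.

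The 56-day ceiling assumes that a gap is dated when it completes, which 9.7.5 does not say outright. A reader might go on to put a figure on the end-of-life care lost per patient. The protocol does not say how many patients die within 8 weeks of a last dose, or how long after it, so any such figure would be an assumption.

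**What to change.** - State one discontinuation date for analysis purposes, and use it in both the TTD row of Table 3 and section 9.7.5.
- In 9.7.3 and every HCRU and cost row of Table 3, make the windows contiguous. For patients with a discontinuation event (gap, next treatment or death), start window 3 on the day after the last recorded dose and run it to death or censoring. For patients censored without discontinuation, run window 2 to the censoring date.

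The two groups need separate rules. Starting window 3 after the last dose for everyone would label the ordinary days between doses as post-discontinuation for patients still on treatment.

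In the four illustrative patients this gives windows 2 and 3 of 168 and 132, 168 and 20, 168 and 35, and 175 and 0 days, with nothing uncovered.

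The cost is a few sentences in 9.7.3 and 9.7.5, matching text in Table 3, and a change to the window programming. No new data are needed. Because the windows serve a primary objective, and section 9.7 reserves major changes to primary endpoint definitions for a protocol amendment, the change belongs in the protocol and should be in place before the final analysis planned for 27 February 2026.
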